PI	Principal Investigator
SADE:	Serious Adverse Device Effect
SAE:	Serious Adverse Events
UADE:	Unanticipated Adverse Device Event

PROTOCOL SUMMARY

Study Title:	A Multicenter Observational Study to Evaluate Outcomes of EmboCube Gelatin Embolization to Control Bleeding or Hemorrhage
Study Objective:	To collect clinical safety and performance outcome data associated with the use of EmboCube Embolization Gelatin to control bleeding or hemorrhage.
Study Device:	EmboCube Embolization Gelatin
Study Design:	Multicenter observational post-market clinical follow-up study in subjects treated with EmboCube
Device Regulatory Status:	CE mark approved March 2019 (CE 667862).
Sample size:	
A minimum of 100 subjects will be included. This sample size is based on a one-sample non-inferiority analysis of Clinical Success based on the parameters listed below and a 15% loss-to-follow-up:
 
 • Reference Clinical Success rate (p_0): 92% • Treatment rate (p): 90% • Non-inferiority margin: 10% • α: 0.05 • Power: 80% 
The reference Clinical Success rate is based on historical clinical literature data for benchmark gelatin embolic devices.

Subject Population:	Subjects who are treated with EmboCube to control bleeding or hemorrhage in accordance with the current approved CE Mark indication for use as stated in the Instructions for Use (IFU).
Clinical Sites:	Up to 7 centers may be included to allow enrollment of required subjects.
Study Follow-Up:	Data will be collected to 28 days post procedure.
Estimated Study Duration:	
First patient enrolled: July 2022
 
Last patient enrolled: July 2023
 
Last patient, last visit: August 2023

Primary Endpoints:	
The primary performance endpoint will be clinical success defined as cessation of bleeding post-embolization and absence of rebleeding at the treated site requiring reintervention (repeat embolization or additional surgery) within 24 hours.
 
The primary safety endpoint will be absence of unanticipated serious adverse device effects within 24 hours.

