7.1 Adverse Event definitions

Adverse events will be classified according to ISO 14155:2020 definitions. Where the definition indicates “investigational medical device”, it refers to the EmboCube Embolization Gelatin used in the index procedure.

Adverse Event (AE): (ISO14155:2020, 3.2)

Untoward medical occurrence, unintended disease or injury, or untoward clinical signs (including abnormal laboratory findings) in subjects, users, or other persons, whether or not related to the investigational medical device and whether anticipated or unanticipated.

Note 1 to entry: This definition includes events related to the investigational medical device or the comparator.

Note 2 to entry: This definition includes events related to the procedures involved.

Note 3 to entry: For users or other persons, this definition is restricted to events related to the use of investigational medical devices or comparators.

Adverse Device Effect (ADE): (ISO14155:2020, 3.1)

Adverse event related to the use of an investigational medical device.

Note 1 to entry: This definition includes adverse events resulting from insufficient or inadequate instructions for use, deployment, implantation, installation, or operation, or any malfunction of the investigational medical device.

Note 2 to entry: This definition includes any event resulting from use error or from intentional misuse of the investigational medical device.

Note 3 to entry: This includes ‘comparator’ if the comparator is a medical device.

Serious Adverse Event (SAE): (ISO 14155:2020 3.45)

Adverse event that led to any of the following:

- a) death,
- b) serious deterioration in the health of the subject, users, or other persons as defined by one or more of the following:
 - 1) a life-threatening illness or injury, or
 - 2) a permanent impairment of a body structure or a body function including chronic diseases, or
 - 3) in-patient or prolonged hospitalization, or
 - 4) medical or surgical intervention to prevent life-threatening illness or injury, or permanent impairment to a body structure or a body function,
- c) foetal distress, foetal death, a congenital abnormality, or birth defect including physical or mental impairment

Note 1 to entry: Planned hospitalization for a pre-existing condition, or a procedure required by the CIP, without serious deterioration in health, is not considered a serious adverse event.

Serious Adverse Device Effect (SADE): (ISO 14155:2020 3.44)

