Adverse device effect that has resulted in any of the consequences characteristic of a serious adverse event.

In addition to the ISO14155:2020 definitions, the following study specific definitions apply:

Procedure-Related Adverse Event: an adverse event is considered to be procedure-related when, in the judgment of the Investigator, it is reasonable to believe that the event is associated with the assigned study procedure and is not solely to the device. Other products, surgical techniques, or medications required specifically for the procedure are likely to have contributed to the occurrence of the event.

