9.2 Primary Endpoint Analysis

Endpoints will be analyzed using the intention-to-treat analysis set. An additional supportive analysis will be conducted in the PP analysis sets for the primary safety and effectiveness endpoints. All available data will be used for each endpoint and no imputations will be done.

The primary endpoint of clinical success will be presented as frequency and percentage.

The primary safety endpoint of absence of SADE within 24 hours, will be presented as frequency and percentage.

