7.1.2 PRIMARY SAFETY ENDPOINT

The primary safety endpoint will be the absence of unanticipated serious adverse device effects within 24 hours.

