8.2 PRIMARY DATA ANALYSES

Endpoints will be analyzed using the ITT analysis set. Additional supportive analyses will be conducted in the PP analysis sets for the primary safety and effectiveness endpoints. All available data will be used for each endpoint and no imputations of data are planned.

The primary endpoint of clinical success (defined as cessation of bleeding post-embolization and absence of re-bleeding at the treated site requiring re-intervention [i.e., repeat embolization or additional surgery], within 24 hours) will be presented as frequency and percentage.

Endpoint Derivation:

- “Was there a re-intervention to treat bleeding?” is checked NO, **AND**
- “Was occlusion of the treated area (as seen on post-embolization angiogram) successful?” is checked YES, **AND**
- “Did subject have any re-interventions post-procedure through 24 hours post-procedure?” is checked NO

The primary safety endpoint of absence of serious adverse device effect within 24 hours will be presented as frequency and percentage

Endpoint Derivation:

- “Did any serious and device- and/or procedure-related adverse events occur during the procedure or up to 24 hours post-procedure?” is checked NO

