9 TABLES, LISTINGS, AND FIGURES

9.1 PLANNED TABLES

The planned tables are provided below. Additional tables may be added to the reporting at the discretion of the Biostatistician in consultation with the Project Manager.

- Demographics and baseline characteristics (ITT)
- Medical history (ITT)
- Medications (ITT)
- Blood tests/coagulation status (ITT)
- General procedure characteristics (ITT)
- Embolization procedure characteristics (ITT)
- General re-intervention procedure Information (ITT)
- Primary endpoints—Clinical success and absence of unanticipated serious adverse device effect within 24 hours (ITT)
- Primary endpoints—Clinical success and absence of unanticipated serious adverse device effect within 24 hours (PP)

- Secondary endpoints—Incidence of adverse events, technical success, and incidence of device observations related to EmboCube (ITT)
- Secondary endpoints—Incidence of adverse events, technical success, and incidence of device observations related to EmboCube (PP)
- Safety summary (ITT)
- Subject disposition (ITT)
- Protocol deviations (ITT)
- Device observations (ITT)

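### The primary safety endpoint is titled as freedom from unanticipated serious device effects, but the SAP derives it from a checkbox covering any serious device- or procedure-related event

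*SAP*

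**What the plan says.** **Definition.** Protocol 4.1.2 and the Protocol Summary state: "The primary safety endpoint will be absence of unanticipated serious adverse device effects within 24 hours". SAP 7.1.2 agrees: "The primary safety endpoint will be the absence of unanticipated serious adverse device effects within 24 hours". The SAP synopsis (section 3) and the titles of the ITT and PP primary-endpoint tables in SAP 9.1 also keep the word unanticipated.

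**Analysis text.** Protocol 9.2 says "The primary safety endpoint of absence of SADE within 24 hours, will be presented as frequency and percentage", and SAP 8.2 says "The primary safety endpoint of absence of serious adverse device effect within 24 hours will be presented as frequency and percentage". Neither mentions anticipation.

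**Derivation.** Directly below that sentence, SAP 8.2 scores the endpoint as met when one eCRF question is answered NO: "Did any serious and device- and/or procedure-related adverse events occur during the procedure or up to 24 hours post-procedure". No other derivation is given.

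**Event classes.** Protocol 7.1 defines an adverse device effect as "Adverse event related to the use of an investigational medical device". It defines a procedure-related event separately, as one "associated with the assigned study procedure and is not solely to the device".

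**The concern.** One primary endpoint is described in three ways, and the one that will be programmed is the furthest from the title. A serious event caused by the procedure alone is not a device effect under Protocol 7.1, yet it makes the subject a primary safety failure. So does a serious device effect already listed among the IFU complications in Protocol 8.1.

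The checkbox has the event class and window of secondary endpoint 1 as defined in Protocol 4.2 and SAP 7.2. The primary figure would therefore largely restate a secondary one. It would not isolate the unanticipated device effects that Protocol 1.5 says the study is meant to identify.

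Neither document gives a rule for calling an event unanticipated or names who decides. UADE appears in the protocol's abbreviation list but is defined in neither Protocol 7.1 nor Protocol 12.

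The study is mainly descriptive, so the labelled estimate is its product. Protocol 1.5 sends the data to the risk analysis, the clinical evaluation report and labeling, and SAP 8.1.5 plans interim analyses for regulatory submissions.

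**Working it through.** **Step 1: compare the texts.**

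| Where | Unanticipated required? | Device-related required? |
|---|---|---|
| Protocol Summary and 4.1.2; SAP 3, 7.1.2 and table titles in 9.1 | Yes | Yes |
| Protocol 9.2; analysis sentence in SAP 8.2 | No | Yes |
| Derivation in SAP 8.2 | No | No, procedure-related events also count |

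**Step 2: direction.** The three event sets are nested: unanticipated serious device effects lie within all serious device effects (SADEs), which lie within all serious device- and/or procedure-related events. If sites complete the checkbox correctly, the derived event-free rate is at or below the rate the title names. The two are equal only if every flagged subject has an unanticipated serious device effect, or nobody is flagged.

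**Step 3: size.** The documents give no rate, target or event count for this endpoint, so there is no plan figure to reproduce and the counts below are assumptions. N = 100 is the planned minimum; it was sized on clinical success and serves here only as the denominator. Let u be the number of subjects with an unanticipated serious device effect and k the number of other flagged subjects.

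- Titled rate = (N − u)/N
- SAP rate = (N − u − k)/N
- Gap = 100 × k/N percentage points, so 1.0 point per subject at N = 100

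Intervals are two-sided 95% Clopper-Pearson, as SAP 8.1 specifies. For x event-free subjects, the lower limit is the 0.025 quantile of Beta(x, N − x + 1) and the upper limit is the 0.975 quantile of Beta(x + 1, N − x). For x = N the upper limit is 1 and the lower limit is 0.025^(1/100) = 0.964.

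| u | k | SAP derivation | Titled endpoint |
|---|---|---|---|
| 0 | 0 | 100% (96.4–100) | 100% (96.4–100) |
| 0 | 1 | 99.0% (94.6–100.0) | 100% (96.4–100) |
| 0 | 2 | 98.0% (93.0–99.8) | 100% (96.4–100) |
| 0 | 5 | 95.0% (88.7–98.4) | 100% (96.4–100) |
| 0 | 10 | 90.0% (82.4–95.1) | 100% (96.4–100) |
| 1 | 5 | 94.0% (87.4–97.8) | 99.0% (94.6–100.0) |

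All three descriptions can differ at once. Take u = 0, two subjects with anticipated serious device effects and five with procedure-only events. The title gives 100% (96.4–100), the analysis sentence 98.0% (93.0–99.8) and the checkbox 93.0% (86.1–97.1).

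**Step 4: do other planned outputs supply the titled endpoint?** They do not. SAP 8.4 tabulates serious device- or procedure-related events over the whole follow-up, without a 24-hour line for device-related or unanticipated events. SAP 8.3 derives secondary endpoint 1 only from events rated definitely related to device or procedure. That filter is absent from the checkbox, so the two 24-hour figures for the same event class may also disagree.

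**The case against.** The best case for the plan has four parts.

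- **The direction is conservative and nothing is decided on it.** Protocol 9 calls the analysis primarily descriptive, there is no safety threshold, and no stopping rules are pre-stated. Protocol 10.16 lists unanticipated device effects as a possible reason to end the study, but ties this to no rate or endpoint. This stands and limits the seriousness of the point.
- **The missing word in Protocol 9.2 and SAP 8.2 may be shorthand.** That is possible, since the definitions and table titles are consistent. It does not explain the checkbox, which is the main conflict.
- **A reader could recover much of the information.** SAP 8.4 and 9.2 plan adverse-event listings with start date, severity and relationship. This helps, but the items SAP 8.4 specifies include no anticipation field and no time of day, and a listing is not a tabulated endpoint.
- **The rule and assessor may exist elsewhere.** Protocol 10.17 has an independent physician adjudicate serious and potentially device-related events under a charter. Protocol 7 has the sponsor compare events with anticipated rates. Protocol 7.4.2 refers to a separate safety plan. The eCRF, charter and safety plan were not available for review, so the gap is a rule and assessor not stated in the protocol or SAP; it does not show that the endpoint cannot be derived. Protocol 10.17 itself gives the adjudicator no task of classifying anticipation, and the SAP derivation does not refer to adjudication.

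**Conclusion.** The concern holds. Followed exactly, SAP 8.2 places a different and broader quantity under the title of the primary safety endpoint. The error is one of definition and labelling in current text and should be fixed. It affects no hypothesis test and no sample size.

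At N = 100 the understatement is 1.0 percentage point for each flagged subject without an unanticipated serious device effect. It is zero if there are no such subjects. The illustrated counts are assumptions and should not be read as an expected bias. The direction relies on sites completing the checkbox correctly.

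**What to change.** Make one endpoint govern the definition, analysis text, derivation and table titles, and settle it before outcome data are summarized. There are two ways.

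**(a) Keep the titled endpoint.**
- Restore unanticipated in Protocol 9.2 and SAP 8.2.
- Name the reference document against which events are judged anticipated, and the assessor.
- Derive the endpoint from event-level data: onset within 24 hours, seriousness, device relationship and the anticipation classification.
- State which of the four causality levels in Protocol 12 count as device-related, and reconcile this with the definitely-related filter in SAP 8.3.
- Report all SADEs, and all serious device- or procedure-related events, within 24 hours as separate lines beside the whole-follow-up summary in SAP 8.4.

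The cost is wording in both documents, minor programming, classification of serious events in subjects already enrolled, and one added assessment or data item unless the eCRF already holds it.

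**(b) Keep the checkbox.** Reword the Protocol Summary, Protocol 4.1.2 and 9.2, and SAP 3, 7.1.2, 8.2 and 9.1 to name any serious device- and/or procedure-related event within 24 hours. The cost is wording only. However, the study then has no primary endpoint specific to unanticipated device effects. The primary endpoint also duplicates secondary endpoint 1 as defined, and the SAP 8.3 filter must still be reconciled so that the two figures agree.

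Either option may need a protocol amendment. Under Protocol 10.14, sites (up to 7 centers) implement one only after approval by the EC/IRB, the sponsor and, where applicable, the regulatory authority. Option (a) fits the purpose in Protocol 1.5 better.

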8.3 SECONDARY DATA ANALYSES

All secondary endpoints will be tabulated. Means, SDs, and sample size will be used to summarize continuous variables. Distributions of continuous data will be examined and if non-normality is exhibited, medians and interquartile ranges will be presented. Frequencies and percentages will be used to summarize categorical variables. All available data will be used for each endpoint and no imputations will be performed.

Incidence of adverse events to 24 hours post-operative (serious and device- and/or procedure-related)

Endpoint Derivation:

- Serious adverse events as reported by the site, **AND**
- “Seriousness” is checked as anything other than “Not Serious”, **AND**
- Relationship to study device **AND/OR** relationship to study procedure is “Definitely related”

Incidence of adverse events between 24 hours and 28 days post-operative (serious and device- and/or procedure-related)

Endpoint Derivation:

- “Were there any serious and device- or procedure-related adverse events since the 24-hour contact visit?” is checked YES, **AND**
- Serious adverse events as reported by the site and in which “Seriousness” is checked as anything other than “Not Serious”, **AND**
- Relationship to study device **AND/OR** relationship to study procedure is “Definitely related”

Technical success defined as successful occlusion of the treated site as seen on post-embolization angiography

Endpoint Derivation:

- “Was occlusion of the treated area (as seen on post-embolization angiogram) successful?” is checked YES

Incidence of device observations related to EmboCube

Endpoint Derivation:

- “Was procedure aborted due to device observation?” is checked YES

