7 ADVERSE EVENTS

For the purpose of this Study, all serious and potentially device-related and/or index procedure-related adverse events will be documented to 28 days post-index procedure and reported to Sponsor via the eCRF.

All deaths will be reported to 28 days, regardless of investigator assessment of causality.

The Sponsor shall review all reported adverse events for their relationship to the study device and/or procedures and comparative anticipated safety event rates. The Sponsor will conduct evaluations of any device-related event per standard operating procedures.

An independent Physician Adjudicator will be responsible for review and adjudication of events defined in Section 10.17.

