10.17 Independent Physician Adjudicator

An independent Physician Adjudicator (IPA) will be responsible for review and adjudication of all serious and potentially device-related adverse events, at minimum. Other events may be reviewed as defined in the IPA Charter.

In order to enhance objectivity and reduce the potential for bias, the IPA shall be independent of the Sponsor as well as the investigational sites and investigators. The methodology for performing these responsibilities shall be developed and outlined in the IPA Charter. Operational provisions shall be established to minimize potential bias.

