10.18 Measures to Minimize bias

The following measures will be implemented to minimize the potential for bias in this single arm Registry:

- Sites are requested to screen and enroll consecutive subjects, as far as possible, and enrollment activities will be documented in a screening/enrollment log.
- Multiple sites will be included to ensure a representative sample of physicians performing the procedure and to provide a reasonable enrollment period.
- Site selection will be performed using predefined parameters to ensure Investigators are appropriately qualified to conduct registry.
- Only physicians that are trained and experienced in vascular embolization can participate.
- Site training will be performed to assure full understanding and engagement to comply with the study design and all protocol requirements.
- A sample of adverse events will be reviewed and assessed by an independent Physician.
- Any known or foreseeable factors that may compromise the outcome of the Registry or the interpretation of results are covered by the Inclusion and Exclusion criteria.
- Financial disclosures will be collected from all investigators to document any potential for bias or conflict of interest.

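### The SAP's safety endpoints use site-entered eCRF fields and no adjudicated classification; separately, protocol 10.17 and 10.18 disagree on which events are adjudicated

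*SAP*

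**What the plan says.** Protocol 10.17 makes an independent physician responsible for "review and adjudication of all serious and potentially device-related adverse events, at minimum". The same section gives the purpose: "In order to enhance objectivity and reduce the potential for bias, the IPA shall be independent of the Sponsor", and independent of the sites and investigators too. Section 7 points to that scope: "An independent Physician Adjudicator will be responsible for review and adjudication of events defined in Section 10.17". The method is left to a charter that is not among the documents. Protocol 10.18, in its list of measures against bias, describes the review differently: "A sample of adverse events will be reviewed and assessed by an independent Physician".

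SAP 8.2 derives the primary safety endpoint from one eCRF question, "Did any serious and device- and/or procedure-related adverse events occur during the procedure or up to 24 hours post-procedure", answered no. SAP 8.3 derives the 0 to 24 hour adverse event endpoint from "Serious adverse events as reported by the site", the seriousness field and the relationship field. The endpoint for 24 hours to 28 days first needs a yes to a question on whether any such event occurred. It then takes "Serious adverse events as reported by the site and in which" the seriousness field shows a serious category. In both, an event counts only if its relationship to the device is at the top level, or if "relationship to study procedure is “Definitely related". Protocol section 12 defines four levels of causality.

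Protocol 7.4.1 makes relationship part of the adverse event report on the eCRF, and 10.8 makes the investigator or site staff responsible for recording the clinical data.

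**The concern.** This is a single-arm study in which the treating site records whether an event is serious and related to its own procedure. Section 12 also lets the sponsor assess causality, but the sponsor is not independent either. The adjudicator is the only assessor whom the protocol requires to be independent of both. If the endpoint rules take no input from that assessor, the safeguard is in place but has no effect on the reported safety endpoints. The secondary endpoints are the most exposed, because they turn on one graded judgement: whether an event is definitely related or only probably or possibly so.

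The conflict between 10.17 and 10.18 is a second and separate problem. A site, monitor or adjudicator cannot tell from the protocol whether every qualifying event goes to review or only some of them.

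**Working it through.** 1. Trace each safety endpoint to its inputs.

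| Endpoint | Inputs named in the SAP | Adjudicated value used |
|---|---|---|
| Primary safety, to 24 h (8.2) | One yes/no eCRF question | No |
| Secondary AE, to 24 h (8.3) | Site-reported serious events; seriousness field; relationship field | No |
| Secondary AE, 24 h to 28 days (8.3) | One yes/no eCRF question; site-reported serious events; seriousness field; relationship field | No |

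The SAP itself ties the site to the events and, in the second AE endpoint, to their seriousness. It does not name who sets the relationship field. That this is a site entry follows from protocol 7.4.1 and 10.8.

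2. Look for another route. SAP 8.1.1 takes all data from the EDC system. The safety summary (8.4) reports severity and relationship without naming the assessor. The planned tables (9.1) and listings (9.2) contain no adjudicated result. The supplied SAP does not mention an adjudicator and has no rule for disagreement.

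3. Compare the scopes. Protocol 10.17 covers all qualifying events and calls that a minimum, and section 7 defers to it. Section 10.18 covers a sample. Both cannot be followed. This conflict does not cause the gap in steps 1 and 2: with every event adjudicated, the three derivations would still read the same fields.

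4. Compare the adjudication scope with the endpoint scope. All three derivations count procedure-related events. If 10.17 means events that are both serious and potentially device-related, events related only to the procedure count in the endpoints but lie outside the adjudicator's minimum.

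5. Work out which way adjudication could move each endpoint. Under protocol 7.2 and 7.3, sites report events that are serious and potentially related, plus all deaths. Other events that a site judges unrelated or not serious never reach the adjudicator. The primary question already counts any serious device- or procedure-related event, so adjudication could mostly only remove events. The exception is a death that the site called unrelated. The secondary endpoints can move either way: a reported event graded possible or probable may be raised to the top level, and one at the top level may be lowered.

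6. Size. The plan states no expected safety rate to reproduce, so the event counts x are assumptions. SAP 8.1 specifies the Clopper-Pearson 95% interval, with lower limit BetaInv(0.025; x, n−x+1) and upper limit BetaInv(0.975; x+1, n−x). The planned minimum is n = 100. As a second case, the stated 15% loss leaves 100 × 0.85 = 85.

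| x | n = 100 | n = 85 |
|---|---|---|
| 3 | 3.0% (0.6% to 8.5%) | 3.5% (0.7% to 10.0%) |
| 5 | 5.0% (1.6% to 11.3%) | 5.9% (1.9% to 13.2%) |

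At n = 100, one subject is one percentage point. The upper limits for 0, 1, 2 and 3 events are 3.6%, 5.4%, 7.0% and 8.5%, so one reclassified event moves the upper limit by 1.8, 1.6 or 1.5 points.

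**The case against.** The protocol promises review and adjudication. It does not say that the adjudicated classification drives the endpoints, so using the site's classification is a permissible choice. The charter might settle how adjudicated values enter the database, and they might overwrite the site's fields in the EDC system. The sponsor also reviews every reported event for relatedness (protocol section 7). The analysis is descriptive, and no test or decision rule depends on these rates. Adjudication also cannot correct the filter that matters most, which is whether the site reports an event at all.

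Much of this stands, and it rules out three stronger readings. A reader might infer that 10.18 cuts adjudication to a sample and thereby keeps it out of the results. The documents do not support that: 10.18 contradicts 10.17 without amending it, and the SAP gap exists under either scope. A reader might infer that the site's judgement is final, but the sponsor also has a role in causality. A reader might infer that adjudication can never reach the results. Without the charter, that cannot be shown.

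The objection does not remove the narrower point. The SAP is where endpoint rules belong. It names site reports and eCRF fields, and it is silent on the adjudicator. If site classification is the deliberate choice, the SAP should say so and say what the adjudication is for.

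**Conclusion.** Two separate points hold. First, the supplied SAP derives the primary safety endpoint and both secondary adverse event endpoints without any adjudicated classification or disagreement rule, so full adjudication would change none of them as written. This rests on the SAP text supplied, on protocol 7.4.1 and 10.8 for the relationship field being a site entry, and on nothing in the unseen charter overriding the SAP. Second, protocol 10.17 and 10.18 contradict each other on scope and must be reconciled.

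The possible effect is modest and uncertain. A shift from 3 to 5 events, as in the table, is an illustration for the secondary endpoints only and could equally run the other way. It should not be read as an estimate or applied to the primary question. Technical success and device observations are not adverse event endpoints and are not affected. The analyses can run without a change, but the change should be made before the final safety analysis.

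**What to change.** In SAP 8.2 and 8.3, use the adjudicated seriousness and relationship for every event within the adjudication scope. Keep the site's classification for events outside the scope, and flag them so that the mixture is visible. For the primary endpoint, this means deriving the result from the event records and not from the single question alone. Show the result based wholly on site classification as a sensitivity row, and add a table of site against adjudicator classification to the list in 9.1.

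In the protocol, align 10.18 with 10.17, and state whether events related only to the procedure are within the adjudicator's scope, since they count in these endpoints.

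The cost is wording in both documents and one small table. The adjudicator is already required and no new subject data are needed. If procedure-only events are brought into scope, the charter and the adjudicator's workload may grow. The final safety analysis would have to wait for adjudication to finish. The change will not recover events that sites did not report.
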